participants are fully aware of these risks before deciding whether to enroll in the study. There is also always the risk of technical difficulties resulting in failure to receive or send messages.

Risks to Infants. If study participants are engaging in hazardous drinking and/or breastfeeding while drinking, their infant children may be at risk. To mitigate this risk, we will take the following steps, based on prior text-messaging research studies with high-risk populations. First, we will use the baseline training session to educate study participants on the risks associated with drinking and breastfeeding. The TMI will also include messages providing psychoeducation regarding the risks of drinking while breastfeeding.. At the beginning of the study, we will provide participants with a list of local treatment providers and support groups that they can access if they choose to. Drinking while breastfeeding is not reportable as child abuse.

Potential Study Benefits

Study participants may or may not benefit directly from participating in this study. It is possible that some participants may benefit from the supportive text messages they will receive because they may find the messages to be supportive and helpful. The primary benefit of the study will be in terms of the knowledge gained and the potential for improving reach to postpartum women who struggle with alcohol, an important and currently underserved group. The knowledge gained as a result of this study will be invaluable to future efforts to provide interventions directly to postpartum women to address risky drinking and other negative health behaviors. Postpartum women are a currently underserved population at high risk for negative consequences of drinking and are unlikely to be reached by the formal service system. Text messaging represents a potential low cost and low burden approach for reaching this population, with potential large impact in terms of reach and scalability. The risks to study participants are reasonable in relation to anticipated benefits. Procedures have been developed and will be in place throughout the study to minimize these risks to the greatest degree possible. These procedures have been successful in preventing risk in past studies using similar procedures.

PROTECTIONS AGAINST RISK

General Protections Against Study Risks

If the baseline assessment indicates very severe substance use or psychiatric problems that would not be adequately served by the TMI provided as part of the proposed study, the participant will be referred to local inpatient or outpatient treatment providers or to another appropriate care facility. We will develop an information sheet with information on local treatment providers and support groups and provide this to participants at the beginning of the study, and again at the baseline assessment if the baseline assessment reveals substance use or psychiatric problems at the level that would not be adequately served by the TMI provided in the study. Risks to infants, such as risks associated with drinking while breastfeeding, will be addressed through provision of psychoeducational information to participants during the baseline training session, as well as regularly throughout the intervention period via text message.

The issues surrounding confidentiality are of supreme importance and sensitivity because highly personal clinical information will be obtained from participants. Participants will sign a statement that attests to their understanding that the information they provide will be held as confidential to the extent permitted by law. Consent forms will clearly state the right to refuse participation or to withdraw at any time.

In order to address any concerns regarding coercion, clients will be informed that they are free to choose not to participate and may withdraw at any time (this is included in the consent form). In addition, the reimbursement rates of \$25 per interview and \$0.50 per EMA are moderate amounts that are appropriate for the time investment and not considered coercive. Individuals who are hesitant to consent or express the desire to withdraw will not be offered additional financial incentives to continue.

Protection Against Risks Associated with Cell Phone Based EMA and Intervention Delivery

All text messaging for the purposes of participant tracking will occur through Partnership to End Addiction's JITA Master Platform, which has been used in studies by Columbia University, NYU, Northwell Health and the American Cancer Society, and all EMA data collection will occur through Metricwire's Catalyst app.

Partnership's Platform: The Platform uses an Internet Information Server (IIS) structure to authenticate and assign the proper groupings to the logins. At no point does the program ask clients for their name or contact information, other than phone number and email. The Platform Data Services and Web Application are

hosted in Amazon Web Services (AWS) in AWS HIPAA-compliant services. Industry-standard application architecture guidelines and principles are best practices including features such as: Route53-highly available and scalable cloud Domain Name System (DNS) web service, Elastic Beanstalk, Multi-AZ Remote Database Service, Guard duty – continuous security monitoring service that analyzes and processes the following data sources: VPC Flow Logs, AWS CloudTrail event logs, and DNS logs, and Inspector service that enables you to analyze the behavior of your AWS resources and helps you identify potential security issues. In addition, the platform includes best practices in HIPAA-compliant authentication and security (e.g., password restrictions, 2-factor authentication, role based security, and audit logging and reporting).

Participants will be informed of the risks of using their cell phone for research purposes, and informed that it is their responsibility to secure their phone at all times. They will be told that they can delete text messages after reading (and responding when necessary). They will also be reminded that while our databases are secure, all email and SMS communication is as secure as any other email or SMS message they may receive. We will reinforce this risk during recruitment and the consent process, and during the baseline training session.

When a participant enters his/her phone number in the Platform, a unique data identifier will be created automatically. A separate database reference system will be created. All electronic files (e.g., database, spreadsheet, etc) containing identifiable participant information are password protected and restricted only to key study personnel who need access to this information for the purposes of tracking participants through the study. All computers hosting such files have a BIOS password to prevent access by unauthorized users. Research staff will have a secure login to access study data.

Metricwire: We will take precautions to ensure that participants are aware of steps they can take to protect their privacy and include a number of built-in features to protect privacy while using the Catalyst app. Specifically, we will include the following features in EMA and TMI to protect participant security and privacy when using the smartphone app:

- (1) Participants will be provided information about ways to protect their privacy when using their smartphone. We will send a message that contains a link to a webpage with information about security steps participants can take to protect their privacy (<http://www.techlicious.com/tip/9-ways-to-secure-your-smartphone/>). Steps may include setting a password to protect from others accessing their device and not using the app while connected to an unsecured wireless network. We will encourage participants to secure their entire smartphone with the built-in “screen lock.” This can use a variety of identification mechanisms (password, face recognition, or fingerprint) that the participant determines is most convenient. Generally, we will encourage participants to use the lock/password features, but we will not require it because it may act as a barrier to using the app (e.g., if participants forget their password or find it frustrating to enter their password each time they want to open the app).
- (2) We will not retain data on participants’ smartphones. Rather, data will be stored on the Metric Wire secure server, which is backed up on a continual basis. Data will be downloaded daily by the study team and stored on Partnership’s secure server. Data on participants’ smartphones will be deleted within several minutes after the information is captured to the server database.
- (3) All data will be transmitted directly between participants’ devices and the server. Transmissions will be encrypted and will not contain any personally identifiable meta-data.
- (4) At the beginning of the study, we will require all participants to “register” their phone (i.e., verify their credentials) to download the app and sync with the protected server. This will be a one-time event, but will ensure that only participants who pass the inclusion criteria and enroll in the study have access to the app.
- (5) Participants do not have the ability to see their data once it is submitted to the Metricwire secure server. For participant generated data, the EMA application interface functions in one direction only. This helps ensure that the participants’ submitted data remains secure even if the device is lost or stolen. In addition, Metricwire has the capability to prevent the participants’ version of the EMA application from connecting to the secure server in the event the phone is lost or stolen.

All data collected using the Metricwire app is property of Partnership to end Addiction, and the agreement with the vendor explicitly specifies this.

CONFIDENTIALITY

Regarding assessment data and other records, Partnership to End Addiction study investigators have an established set of procedures designed to ensure the confidentiality of study data. All staff at Partnership who participate in research with human subjects is required to complete CITI online training on the protection of human subjects, including confidentiality. Additionally, research staff will be trained on and strictly monitored for adherence to federal guidelines for maintaining the privacy and confidentiality of participants throughout the study. All assessment data will be collected via a computer administration platform. No identifying information will appear on any data collection survey; all data will be coded by participant ID. All study data will be stored in databases on Partnership to End Addiction's secure server, where all participant records will be coded and filed numerically according to a unique project identification number, with no names attached to the database. All study databases will be stored in a secure folder on Partnership's network, with access restricted only to the members of the research team. A master table linking participants to project ID codes will be kept in a separate secure file, with access restricted only to those members of the research team who require client contact information for the purposes of tracking and follow-up. For extra security, this file will be password-protected. Follow-up contacts will be made by project staff under explicit guidelines that preserve confidentiality when telephoning or emailing information to participants. Only the PI and RAs who recruit or follow the participants will have access to identifying information.

We will obtain a Certificate of Confidentiality (COC) from NIH to provide an extra layer of protection to all data collected in conjunction with the proposed study. NIH routinely issues COCs to protect research information provided by study participants from compulsory legal demands such as subpoenas for identifying information. The COC can be used to avoid forced disclosures of information collected in the context of a research study and would thus protect against court subpoena of research data.

PROCEDURES FOR OBTAINING INFORMED CONSENT

Informed consent will be obtained online, via a secure Qualtrics form. Participants can complete informed consent either fully online, or via phone with the study RA. Procedures for both options are described below.

Informed Consent by Phone with Study RA: Study participants will be recruited from Central Intake or social media (Facebook, Instagram, Reddit, NextDoor, BabyCenter) during the last trimester of pregnancy. For clients recruited from Central Intake, Central Intake (CI) providers will briefly introduce the study to potentially eligible clients using a script provided by the study team. If a client is interested, the CI provider will ask for permission to provide her contact information and due date to the study team. Within two weeks of the due date, the RA will contact interested clients by phone to screen for eligibility, describe the study, and obtain informed consent. Eligibility screening will include administration of the T-ACE alcohol risk screener with supplementary questions. At the end of eligibility screening, if the participant is eligible, the RA will ask the participant if they are interested in enrolling in the study. If the answer is yes, the RA will send the participant a link to the secure Qualtrics informed consent form via email or text (whatever the participant prefers). The RA will allow them a few minutes to read it, and then review the main points in each section and answer any questions the participant has. The confidentiality that surrounds research studies will be discussed with clients, explaining that confidentiality is assured to the extent permitted by law. This means that the information they provide is confidential, except for the case of potential abuse of a child, or danger to their lives or the lives of others. Given the remote nature of the study, it is extremely unlikely that study staff would become aware of any information that would necessitate breaking confidentiality, such as child abuse or danger to themselves or others. The only way we would become aware of child abuse or neglect is if (1) a participant tells us directly during a phone contact or focus group, or (2) we witness a child being harmed during a zoom focus group in which a participant has their video camera on. Reports of drinking behaviors do not automatically rise to the level of child abuse reporting. Participants will also be informed about the protections afforded by the Certificate of Confidentiality. Participants will be informed that information collected from the EMA, TMI, focus groups, and baseline follow-up assessments will be used only for research purposes and reported in aggregate form (i.e., the confidentiality of individuals will be maintained). Following review of the consent form, the RA will ask if the participant has any questions. If the participant would like to provide consent to enroll in the study, the RA will ask them to complete the questions in the Qualtrics form that assess understanding of the consent form and then click the box labeled "I consent to enroll in the study" to enroll. Participants who are recruited

from social media will also be provided the option to connect with the study RA via phone to complete eligibility screening and informed consent. For participants who select this option, the steps detailed above will be followed.

Informed Consent Online: Participants who click on a social media ad will be directed to the study website, where they will view information about the study and will be prompted to click on a link to complete eligibility screening. Clicking on the link will take them to a secure Qualtrics survey that contains the eligibility screening questions. After answering the questions, eligible participants will be presented with an electronic consent form, in a secure Qualtrics form. The form will provide the name of the PI ([name]) and her contact information and inform respondents that she, as the PI, has IRB approval to conduct the study. The consent form will contain a thorough description of the research project, including the procedures involved, the risks and benefits, compensation, the right to non-participation, and the Research Subject's Bill of Rights. All information described above regarding confidentiality and mandated reporting will be included in the consent form. At the beginning of the consent Qualtrics form, there will be a link to a video that participants must view in order to complete the consent process. In the video, the study RA will review the consent form the same way they do with participants who complete the consent process via phone. To assess understanding of the information provided in the informed consent, eligible participants will be asked a series of multiple-choice questions regarding the informed consent before being able to proceed with the study. Answers will be collected and any wrong answer will result in the potential participant being prompted to review the full consent document before attempting the consent questions again. Potential participants will not be enrolled in the study if they answer the questions incorrectly four times. After completing the questions correctly, participants will be asked to check a box to indicate whether they would like to enroll in the study. Participants who enroll will be prompted to enter their first name and cell phone number into the secure Qualtrics form to allow the study RA to contact them for the Baseline Assessment and EMA training. At any time during the online consent process, participants will have the option to text "BABY" to the study number to contact the study RA to ask questions and/or to complete the consent process via phone.

DATA SHARING

As an NIAAA-funded study, this study is bound by the requirement that all NIAAA-funded human subjects research studies participate in the NIAAA Data Archive. The purpose of the Data Archive is to promote data sharing across the scientific community. NIAAA requires that certain language be included in the informed consent forms to allow participants to make an informed decision about whether they agree to include their data in the Data Archive. Participants who do not agree to have their data included in the Data Archive can still participate in the study. Participants who initially agree to have their data included have the right to change their minds at any time during the study, as stipulated in the consent form. However, once a participant's data is part of the NIAAA_{DA}, the study researchers cannot take back the study data that was shared before they were notified that the participant changed their mind.

Participant information that is entered into the Data Archive is coded according to a "Global Unique Identifier" or "GUID." According to the NIAAA Data Archive, the GUID is a subject ID that allows for the linking of data from a unique individual across multiple studies, but does not expose any personally identifying information. The GUID is generated based on the following information: full name at birth, sex, date of birth, city of birth. All of this information is collected by the research team, who uses the NIAAA GUID Tool to create the GUID. The participant's study data is then submitted to the Data Archive along with the GUID. No identifying information about any study participant is submitted to the Data Archive at any time.

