Step 1: Baseline Assessment. Participants who sign informed consent will be asked to complete a Baseline Assessment via Qualtrics. Participants will be sent a secure link to the Qualtrics survey via text or email. The Baseline will take approximately 30 minutes to complete and will include questions about demographics, parenting, mental health, stress and coping, motivation, and drinking and other substance use.

[figure not shown]
Step 2: Catalyst Training. Following completion of the Baseline, participants will participate in a one-on-one 15-minute training session with the RA via Zoom to provide training on how to download and use the Catalyst app. In order to avoid fraudulent participants, participants will be asked to turn on their camera for 1 minute of the training, after which they will be allowed to turn off their cameras for the remainder of the training if that makes them more comfortable. Participants who complete both the baseline survey and the Catalyst training session will receive a \$25 Amazon gift card upon completion of the Catalyst training session.

Step 3: 28-day MRT. After completing the training, the TMI sequence of EMAs and TMI text messages will begin as described below and will last for 28 days.

TMI Sequence and Randomization

Upon completion of the Catalyst training, the TMI sequence of EMAs and TMI component delivery will begin (see Figure 2).

Figure 2. TMI Sequence

There will be two decision points per day. Decision points will be randomly selected within a 12 hour window starting at the participant's pre-selected start time. There will be at least 4 hours between the two decision points. At each decision point, participants will receive the "decision point EMA." Upon completion of the decision point EMA, participants will be randomized to one of three options: (1) a maternal-focused message (.40 probability); (2) a drinking-focused message (.40 probability); or (3) no message (.20 probability). Fifteen minutes after randomization, participants will receive the "proximal outcome EMA." This sequence will repeat 2 times per day, at each decision point. Participants will also be sent a "morning survey" each morning within 30 minutes of their selected start time that will ask questions about the prior day. After each survey prompt, the survey will be

available for up to 60 minutes, with 2 reminder prompts sent (every 20 minutes). Surveys that are not completed within the 60 minute window will expire.

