Drawing from other EMA feasibility studies²²⁻²⁷, feasibility outcomes will include the percent of EMA surveys completed each day, each week, and at the end of the 14-day period; the percentage of each EMA measure completed; and the percentage of respondents who completed 50% and 80% of EMA surveys^{22,23}. Acceptability measures will be collected via a short text-based survey at the end of the 14-day EMA period and will include assessment of technical challenges, burden, emotional response, and overall satisfaction, using Likert-scale items from other EMA studies²⁴⁻²⁷.

Morning Survey Measures:

[Sent daily at participant-selected wakeup time.]

Construct	Items
EMA Burden/ Acceptability questions [include]	Retrospective questions 1=not at all, 7= very much Burden: 1. Answering to the questions disrupted my everyday life

in final daily diary at end of study]	
 2. The questionnaires on the phone stopped me from doing my usual activities 3. I found it embarrassing when the alarm sounded around other people 4. I enjoyed using the app 5. I found it stressful to use the app 6. Did your motivation to respond to the notifications decrease during the weeks? 7. How tiring was it to take part in this study? 8. Did the questionnaire become boring during the day? 9. Did you get irritation while filling in the questionnaire? 
Ease of use
 
 1. The questionnaires on the phone were easy to complete/ 2. At times I had to rush to complete the questionnaire on the phone on time 3. I found it easy to remember to carry the phone with me during the time of the study
How much time did you spend with your baby yesterday?	
 1. Most or all of the day 2. About half of the day 3. Less than half of the day 4. Evening and night only 5. None 6. Other 
 a. For "how much time did you spend with your baby yesterday" you selected other. Please write in your response below.
Prior night sleep ²⁸	
 1. How well did your baby sleep last night (0 = poor to 7 = excellent) 2. How well did you sleep last night [0 = poor to 7 = excellent]

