Discrimination	
1. At any time yesterday did you feel that you were treated unfairly? (yes/no)
 
2. What was the main reason(s) for the unfair treatment that you experienced yesterday? (check all that apply)
 
 a. Your age b. Your gender c. Your race d. Your ethnicity or nationality e. Your religion f. Your height or weight g. Some other aspect of your appearance h. A physical disability i. Your sexual orientation j. Your drinking k. Your smoking l. Your other substance use m. Being poor n. Being a mother o. Other 
i. For "What was the main reason(s) for the unfair treatment that you experienced yesterday?" you selected other. Please write your response below:
 
3. Who treated you unfairly yesterday? (check all that apply)
 
 a. Family member b. Partner c. Stranger d. Acquaintance e. Employer f. Health care provider g. Other social service provider h. Other _____ 
i. For "Who treated you unfairly yesterday?" you selected other. Please write in your response below:

Decision Point/Daily EMA

[sent 2x daily]

Construct	Items
	
1. Were you with your baby since the last survey you completed? Yes/no [IF NO: Skip Baby Fussiness]
 
2. Will you be with your baby in the next hour? Yes/no [IF NO: Skip Maternal SE]

Maternal SE	How confident are you that you will be able to meet your baby's needs (such as needs to be fed, changed, soothed, or entertained) over the next hour? [Not at all confident to extremely confident 1-7]
Drinking SE ³³	How confident are you that you can avoid drinking for the next hour? [1 = not at all confident to 7 = extremely confident]
Stress ³⁴	Rate your overall stress level right now 1-7, very low to very high.
Mood	
1. What is your overall feeling right now [very unpleasant to very pleasant 1-7]
 
2. What is your overall energy level right now [very low to very high 1-7]
 
3. What is your anxiety level right now [very low to very high 1-7]

Fatigue ¹⁶	
1. How physically exhausted are you right now?
 
2. How mentally exhausted are you right now?
 
[not at all to extremely 1 -7]

Baby Fussiness ³⁵	
1. Since your last assessment, how many times did your baby fuss, cry, or seem upset? [0, 1, 2, 3, 4, 5, 6, 7, 8, 9, 10 or more times]
 
2. How many of these times were you able to successfully soothe your baby? [all of them, most of them, some of them, a few of them, none of them]

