Intent to Drink ³³	How committed are you to not drink in the next hour? [1 = not at all to 7 = extremely]
Urge to Drink	How strong is your urge to drink right now? 1= very low, 7=very high

Drinking	4. Did you consume any alcohol in the past hour? Yes/no 5. If yes, how many drinks did you consume?
----------	--

Proximal Outcome EMA

Construct	Items
Maternal SE	How confident are you that you will be able to meet your baby's needs (such as needs to be fed, changed, soothed, or entertained) over the next hour? [Not at all confident to extremely confident 1-7]
Drinking SE ³³	How confident are you that you can avoid drinking for the next hour? [1 = not at all confident to 7 = extremely confident]
Intent to Drink ³³	How committed are you to not drink in the next hour? [1 = not at all to 7 = extremely]
Urge to Drink	How strong is your urge to drink right now? 1= very low, 7=very high
Drinking	6. Did you consume any alcohol since the last survey you received? Yes/no 7. If yes, how many drinks did you consume?
Stress coping	1. Since the last survey you completed, did you use any strategies to cope with negative feelings or stress? a. I didn't experience negative feelings or stress since the last survey b. I drank alcohol c. I changed my thinking d. I changed my current situation to cope with negative feelings or stress e. I found something else to do f. I sought advice or support g. I came up with a plan to cope with negative feelings or stress h. I set a goal or kept track of my progress towards my goal i. I directly communicated my needs to others j. I tried to relax k. I took medication l. I pushed negative feelings or stress away m. I used another strategy n. I didn't use any strategies to cope with negative feelings or stress 2. In the previous question you indicated that you took medication to cope with negative feelings or stress. Was this medication intended for the purpose of managing negative feelings or stress/for the purpose of managing alcohol cravings? a. Yes b. No 3. Was this medication prescribed to you by your healthcare provider? a. Yes b. no 8. You selected "I used another strategy to cope with stress". Please describe what you did below:

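### The morning survey can overlap the day's first decision point, so look-back items anchored to the last survey sometimes start after randomization or shrink to minutes

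*Combined protocol and SAP*

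**What the plan says.** Under TMI Sequence and Randomization: "Decision points will be randomly selected within a 12 hour window starting at" the start time that the participant chose in advance. The spacing rule reads "There will be at least 4 hours between the two decision points"; no other spacing rule appears in the text. The same section sends the morning survey "each morning within 30 minutes of their selected start time", without saying whether that means before, after or either. The Morning Survey Measures table says instead "Sent daily at participant-selected wakeup time". Every survey stays open for 60 minutes after its prompt and then expires. Randomization follows completion of the decision point EMA, and the proximal outcome EMA is sent 15 minutes later.

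The look-back wording differs by item:

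- **Decision point EMA, Baby Fussiness:** "Since your last assessment, how many times did your baby fuss, cry, or seem upset". A preceding question on whether she was with her baby runs from the last survey completed. A negative answer skips the fussiness items.
- **Proximal outcome EMA, stress coping:** "Since the last survey you completed, did you use any strategies to cope with negative feelings or stress". The drink-coping item uses the same anchor.
- **Proximal outcome EMA, drinking:** runs from the last survey received, whether or not it was completed.

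The protocol calls the morning questionnaire a survey, and nothing excludes it from these anchors.

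**The concern.** The proximal EMA is sent only after a completed decision point EMA. In the normal sequence, the last completed survey is therefore the one that triggered randomization, and the coping look-back starts at randomization. This is the right window for the comparison in MRT Data Analysis, which contrasts the proximal outcome by whether a component was delivered. A morning survey completed in between breaks the anchor, and coping used soon after the message drops out of the reported period. For the drinking item, mere receipt of the morning prompt is enough.

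Self-regulation is one of the three named proximal outcomes, and the coping items appear to be its measure in the proximal EMA, although the text does not map them explicitly. A pilot meant to test methods for a fully powered MRT could also carry the wording forward.

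**Working it through.** The plan gives no figure for this overlap, so there is none to reproduce. The check has two parts: whether the sequences can occur, and how often.

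**Can they occur?** Times are minutes after the start time.

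1. *Look-back of minutes.* Morning survey completed at +20, decision point prompt at +25, decision point EMA completed at +27. The baby items cover 27 − 20 = 7 minutes.
2. *Look-back starting after randomization.* Decision point at +5, EMA completed and woman randomized at +7, morning survey completed at +15, proximal EMA at 7 + 15 = +22. The coping items cover +15 to +22, and the first 15 − 7 = 8 minutes after randomization are lost.
3. *Reset by receipt alone.* Randomized at +7, morning prompt received at +20, proximal EMA at +22. The drinking item covers 2 minutes.

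All three satisfy every stated timing rule.

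**How often?** Inputs from the protocol: a 12-hour window, a 4-hour minimum gap, 60 minutes of availability, a 15-minute delay, 28 days and 50 women (50 × 28 = 1,400 person-days). The rest is assumed:

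- First decision point: (a) the earlier of two uniform times at least 4 hours apart, giving P(first < t) = 1 − ((8 − t)/8)² with t in hours; or (b) uniform over the first 8 hours, giving P(first < t) = t/8.
- Morning prompt: at the start time, or uniform over 0 to +30, −30 to +30, or −30 to 0 minutes.
- All surveys are answered, with a delay uniform over 0–20 or 0–60 minutes.

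First decision point while the morning survey is available (whether or not already answered):

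| Morning prompt | (a) | (b) |
|---|---|---|
| At start time | 1 − (7/8)² = 23.4% | 1/8 = 12.5% |
| 0 to +30 | 22.6% | 12.5% |
| −30 to +30 | 20.2% | 11.0% |
| −30 to 0 | 17.8% | 45/480 = 9.4% |

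In the last row the survey is still open for t = 30 to 60 minutes after the start time (mean 45, mean square 2,100). Under (a) this gives 2 × 45/480 − 2,100/480² = 0.1875 − 0.0091 = 0.178. The overall range is 9.4% to 23.4% of days, or about 131 to 328 of 1,400 person-days.

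Simulated frequencies over the first three prompt assumptions (2,000,000 draws each):

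- Morning survey completed between randomization and completion of the proximal EMA: 0.7% to 6.7% of days, about 10 to 94 person-days. With two decision points a day, this is about 0.3% to 3.4% of scheduled decision points.
- Morning prompt received between randomization and the proximal prompt: 0% to 2.6% of days.
- First decision point look-back of 15 minutes or less: 1.8% to 5.7% of days.

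If the morning prompt always came early, the first of these would be below 2%. The −30 to +30 case is an equal mix of its two halves, so the largest value for the early half is 2 × 4.25% − 6.73% = 1.8%.

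**The case against.** The strongest reply is that overlap is not harm. Self-efficacy, commitment and urge are asked about the next hour or the present moment, and drinking in the decision point EMA about the past hour. None of these moves. The schedule does not depend on the randomized option, so the disturbance is mainly noise, in a pilot that will interpret effect sizes and not significance. Look-backs vary in any randomly timed EMA: skipped surveys and the optional nighttime sequence also move the anchor, and without a morning reset the first look-back could run overnight. Figure 2, which depicts the sequence, is not shown and may contain a timing rule.

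Most of this stands and limits the point to the first decision point of the day and a few items. It does not answer the proximal coping items, whose anchor would otherwise be the randomization time itself.

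Stronger readings are tempting but unsupported:

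- *Up to 29% of days fall in the open window.* That figure, from (a) with the prompt at 0 to +30, counts every first decision point before the morning survey closes. It includes days when the point fires before that survey is sent. While the survey is available, the figure is 22.6%.
- *A tailoring variable is corrupted.* The Study Purpose and Aims section names stress, negative mood and self-efficacy as tailoring variables and treats baby irritability as a trigger. Randomization uses fixed probabilities of .40, .40 and .20, and fussiness is not in the main-effects model.
- *Stacked notifications will reduce completion.* This is plausible, but nothing in the documents shows it.
- *The comparison is biased.* A message might prompt a woman to open the pending morning survey, so look-back length could differ by option. That is a possibility only.

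**Conclusion.** The point holds as a measurement weakness of limited size. The text permits the overlap, and the item wording turns some of it into a wrong or very short look-back. The first decision point falls while the morning survey is available on about 9% to 23% of days. The coping look-back starts after randomization on about 1% to 7% of days, or less if the morning prompt always precedes the start time. These frequencies rest on assumed uniform timing and full response; they are not document figures. The likely effect is added noise in the coping and since-last-survey drinking outcomes, with no demonstrated effect on any estimate. If Figure 2 or the app already separates the two surveys, the text need only say so.

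**What to change.** 1. In the proximal outcome EMA, anchor both coping items and the drinking item to the decision point EMA, for example: since the survey about 15 minutes ago, just before this one. This removes the reset without touching the schedule.
2. In the decision point EMA, use one named anchor for both the time-with-baby question and Baby Fussiness, in place of the present two.
3. Optionally, open the decision-point window at a fixed offset after the latest morning-survey expiry, 30 + 60 = 90 minutes after the start time. State the direction of the 30 minutes and align it with the Morning Survey Measures table. The offset should not depend on completion of the morning survey, which would make decision-point timing depend on participant behaviour. The offset prevents overlap but not a short gap after a late morning survey, so items 1 and 2 are still needed.
4. For data collected under the present wording, compute each look-back from the survey timestamps and flag affected sequences.

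The cost is a few item wordings and, if the offset is adopted, one app setting. The offset's drawback is that the first 90 minutes after the start time are not sampled. If the end of the window stays put, 12 − 1.5 = 10.5 hours remain, which still accommodates the 4-hour gap.
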